#### 4.2 Secondary objective

To determine the efficacy of two-layer Lite compression bandaging for the management of leg ulcers at 6 and 12 weeks post-baseline

- Wound status (healed vs non-healed at 6 weeks)
- Healing rate (ulcer size, PUSH score)
- Leg ulcer related quality of life score (VEINES-QoL)

- Leg ulcer related pain and pruritus levels
- Generic quality of Life (EQ-5D-5L)

## 5. STUDY PROTOCOL

#### 5.1 Study design and timeline

This concerns a multi-centre, controlled prospective randomized study. The study will be carried out in Cumbria by North Cumbria Integrated Care NHS trust and North Cumbria CCG. Up to two other NHS Trusts will be considered for inclusion in the trial as recruitment sites once the trial has been listed on the National Institute for Health Research national portfolio. The study will take place in local community and hospital settings with support and oversight from research staff. Research delivery staff will be delegated to provide support with data collection and processing.

Month	Setup	Recruitment	Analysis	Finalise
Sep-22	Submission for			
	HRA approval			
Sep-22	NIHR portfolio adoption			
Oct-22	HRA and Trust	Start recruitment;		
	approval	first patient, first visit		
May-24		Finish recruitment		
Jul-24		Last participant, last		
		visit		
Aug-24			Analyze data	
Sep-24				Finalise analysis & report

Table 2. Anticipated timeline

## 5.2 Participant identification & screening

Patients who are referred to the local clinical team with a leg ulcer will be screened for eligibility for this study by the direct care team. The research team will then be informed on potential participants and the patient information sheet will be added to the appointment letter. All eligible patients will be invited to take part until the required numbers have been achieved. Patients will be recruited sequentially and randomised into two groups: either the Andoflex or Coban2 bandaging described in section 3 of this protocol. The eligible patient population is defined in the Inclusion and Exclusion criteria section.

There may be occasions where the consent may be delegated to a member of the research team; this is an option as long as the patients has given verbal consent for this when asked by the direct care team first. During the first appointment, the study will be discussed in further detail and the participant has the opportunity to ask questions that they may have. If potential participants meet the eligibility criteria, the patients can be consented by the direct care team personnel or this may

be delegated to the research delivery team (again, as long as the patient's verbal consent has been sought for the latter arrangement). A screening form will be completed for potentially eligible patients to confirm that they indeed meet the trial criteria.

Participants will receive no incentives and consent will be regarded as a process and not a one off event. Participants are free to withdraw from the study at any time without the need to give any reasons for withdrawal. Their standard care will not be affected by either declining to participate in the study or withdrawing during participation – patients would still be managed with the two layer Lite compression bandage type even if not in the trial.

#### 5.3 Recruitment

Participants will be randomised to one of two treatment arms. Patients in both groups will be given standard advice on leg ulcers and their management. Stratification by wound size (PUSH score up to and including 10 or PUSH score of 11 or higher) will take place.

All participants will have demographic data obtained and the following measures (table 3):

Weeks	0	2	4	6#	8	10	12#
Baseline measures (demographics,	Х						
medical history, vascular history)							
Ulcer wound status + bandage	Х			Х			Х
use status							
Ulcer size measured with wound	Х			Х			Х
grid							
PUSH score	Х			Х			Х
Visual analogue pain score	Х			Х			Х
Visual analogue pruritus score	Х			Х			Х
EQ-5D-5L	Х			Х			Х
VEINES-QoL	Х			Х			Х
Photo of ulcer (or original index	Х			Х			Х
site); subject to consent by patient							

#### Table 3. Baseline measures

# Allowed to be up to 2 weeks early or late. For all follow-up dates, calculation is based on original enrolment date for patient, even if deviation for one or more follow-up timepoints.

The Pressure Ulcer Scale for Healing (PUSH) tool, see Appendix 1 is a standardised method of assessing and monitoring the severity and healing of both pressure ulcers and venous leg ulcers (Stotts et al, 2001; Ratliff & Rodeheaver 2005). Concerns have been raised regarding the criterion validity and intra-rater reliability of the tool (Pillen et al 2009) however in the absence of other valid tools it provides a comprehensive parallel assessment of the ulcer along with measuring size alone.

VEINES-QoL is a patient reported outcome measure score that focuses on lower limb health, and can be used in patients both with, or without a leg ulcer (Launois 2015)

During the recruitment process the research team acts as a contact point and coordinator for patients requiring information and support. If concerns are raised on participants (mental) wellbeing

based on the home visits or outcome of the assessments, referral of patients/families on to other professional agencies will be done as appropriate and according to the Trust guideline.

#### 5.4 Follow-up and Standard care

Patients are in the study for the planned 12 weeks, even if the index leg ulcer has healed prior to that time point. Apart from the specific research measurements and assessments, the patient will be followed up as they would in normal clinical practice. The vascular or community nurse will redress the leg ulcer as per routine care, and will conduct the measurement of the leg ulcer (grid measurement and PUSH score). The researcher will visit the patient at baseline, week 6 and 12 of study participation to randomise the patient and conduct the questionnaires.

Patients identified in the community (primary care or non-vascular surgery dept) can be invited to participate in the study via the vascular surgery department.

Standard wound care will be provided throughout the trial period, as well as meeting any other medical needs that arise. The SIGN guidelines for leg ulcer care form the framework for management of the leg ulcers (https://www.sign.ac.uk/media/1058/sign120.pdf).

#### 5.5 Outcome measures

#### 5.5.1 Primary outcome measures

Wound status (healed vs non-healed)

In line with the definition used by the VENUS6 trial team, the primary outcome of this trial is time to healing of the reference ulcer, and the definition is: complete epithelial cover in the absence of a scab (eschar) with no dressing required. There is no minimum length of time that the index site has to have been in said condition for when participant present for follow-up study visit.

#### 5.5.2 Secondary outcome measures

#### Clinical outcome measures

- VLU size, measured with Convatec grid tool
- Size and characteristics of VLU, determined with PUSH score
- Pain score
- Pruritus score
- Quality of life score, determined with VEINES QoL score and EQ-5D-5L score.
- Patient withdrawal rates due to change in management (e.g. need for surgery)
- Leg ulcer infection rates

#### 6. SUBJECTS

#### 6.1 Anticipated number of research subjects

Locally, we have healing data available from two previous trials involving venous leg ulcers, namely the PREVUE and APRICOT trials (Jonker et al 2020a, and Jonker et al 2020b). One caveat is that those

studies concerned pure venous leg ulcers and that compression bandaging could be full (40 to 50mmHg) or Lite (20 to 30 mmHg). Nonetheless, from these studies we know that the study followup time points are valid and APRICOT compared Andoflex vs Coban2.

Below a summary is given for the sample size needed. The primary outcome, wound status (healed vs non-healed) is used for sample size calculation. The non-inferiority related sample size calculation has been performed using the calculator at https://www.sealedenvelope.com/power/binary-noninferior/. Power calculations for sample size assume 80% power and 2.5% one-sided confidence interval. The non-inferiority limit is set at 15% in favour of the Coban2 control bandage. The result is shown in Table 4. Since some patients may withdraw over the course of the 12-week trial period, a 10% dropout rate is calculated into the sample size. A 1:1 allocation to the two types of compression bandage will be applied.

	Sample size calculation	
	Intervention Bandage (Andoflex)	Control Bandage (Coban2)
Ulcer healed	65%	50%
Ulcer not healed	35%	50%
	Sample size required without any du Sample size with 10% attrition rate Total of 92 patients: - 46 Patients to receive Ando - 46 Patients to receive Coba	flex

Table 4, Sample size calculations

The CONSORT guidelines require a statement on the number of patients assessed for eligibility (Schulz, Altman & Moher 2010). The number of patients screened but who did not meet the inclusion criteria or who declined to participate will be recorded, as will any patients who are lot to follow-up (Appendix 5).

## 6.1.1 Randomisation and Blinding

Following written consent patients will be allocated at random to the one of two treatment arms, using a non-restricted randomised sequence generated for the whole sample using a free ware randomisation programme, see https://www.sealedenvelope.com/. The randomisation will be stratified by ulcer size, with one group being those with a PUSH score of up to and including 10, or a PUSH score of 11 or higher.

Each next randomisation allocation will be obtained from the sealedenvelope.com account for this PEACH trial. The randomisation will be stratified by ulcer size, with one group being those with a PUSH score of up to and including 10 (LOW PUSH randomisation), or a PUSH score of 11 or higher (HIGH PUSH RANDOMISATION).

Each next randomisation allocation will be obtained from either the LOW PUSH or HIGH PUSH the sealedenvelope.com account for this PEACH trial. The PUSH score is done as part of standard clinical practice and is a swift method (appr. 1 minute to obtain).

Since it will not be known up front how many patients will be LOW PUSH or HIGH PUSH, a total of 60 randomisations will be generated for each stratification, in blocks of 10 randomisations within said stratification. This means 6x10 randomisations for LOW PUSH and also 6x10 randomisations for HIGH PUSH. If one of the stratifications reaches 60 then only the other stratification can be recruited into going forward. It is recognised that random selection does not guarantee representativeness but variables which may affect the outcome variable are more likely to be balanced out and reliability enhanced (Thomas 1990).

As the study involves different looking bandages, it is not possible to achieve blinding for the participants. However, statistical analysis is carried out blinded to group allocation, by persons who have not had contact with study participants.

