Patient population	
 
Pragmatic approach to allow inclusion of wider cohort of patients than those with pure venous leg ulcers (VLU).
 
Therefore, patients with leg ulcer who are suitable for reduced (ie 'Lite') compression are considered for inclusion.
 
Specifically, these are: 
 
VLU
 
Mixed venous and arterial leg ulcers
 
 
 
Suitability for reduced compression is an ABPI of 0.5 -0.8 depending on holistic assessment. ABPI measured within last 3 months is part of the decision making to use reduced (Lite) rather than full compression. Only if ABPI or other diagnostic method (eg pulse palpation and ultrasound diagnostics, toe pressure assessment or arterial imaging) is not available or applicable then provision of solely a clinical assessment is allowed.
 

Sample size	
 
A total of 92 participants, over the age of eighteen, with leg ulcers. Power beta of 80%, one-sided alpha p-value of 0.025, non-inferiority limit 15%. Assumption of 15% difference in absolute percentage healed ulcers in intervention (Andoflex) arm versus control (Coban2) arm.
 
Therefore, 97.5% confidence interval for Andoflex to be no more than 15% worse than mean ulcers healed percentage for Coban2.
 
Sample size with 10% attrition rate included: 92 patients Of which: 
 
46 Patients to receive Andoflex TLC Calamine Lite
 
46 Patients to receive Coban2 Lite
 
 
 
Participants must have the capacity to provide informed written consent and complete patient reported outcome measures. Participants are recruited from the local community nursing caseload and identified in hospital clinics.
 

	Randomisation will be stratified for ulcer size, with cut-off	
	PUSH score of up to and including 10, or 11 and above.	
Sponsor	North Cumbria Integrated Care NHS Foundation Trust	
5001301	North Cumbra integrated care with roundation must	
Manufacturer & funder	Milliken Healthcare Inc	
	UK-based contact: [name], Clinical Specialist EMEA ,	
	Milliken Healthcare Division, [name] ,	
	[contact]	
Chief Investigator	[name], vascular specialist nurse, Vascular Surgery	
	Dept, North Cumbria University Hospitals NHS Trust.	
	[contact]	
Co-investigators	[name] PhD, Research Project Lead, [contact];	
	Cumbria Partnership NHS Foundation Trust	
	R&D Department, Carleton Clinic	
	[name]	
	[contact]	
	[name], GPwSI Research, Cumbria Partnership NHS	

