#### 6.2.2 Exclusion criteria

- Under the age of 18 years
- Unable to fully understand the consent process and provide informed consent due to either language barriers or mental capacity
- Limited life expectancy, i.e. undergoing palliative care, or other condition that in opinion of researcher contraindicates participation

- Active infection in leg ulcer treated with antibiotics within last 1 week (does not apply for prophylactic antibiotic regimes)
- Is not willing or able to wear any compression device
- Pure foot ulcer, ie any ulcer that commences below malleolar region (particularly plantar, digital regions)
- Enrolled in other interventional research study related to patient's leg ulcer
- Previous participation in PEACH trial
- Awaiting surgical intervention related to vascular system of the lower limbs, planned within three months
- Wound size that is too small (typically < 1 cm^2), or too large (larger than single wound grid or extending round the leg) to measure accurately
- Known intolerance or allergy to materials used in compression bandaging (including zinc oxide, calamine).

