#### **Directions:**

Observe and measure the pressure ulcer. Categorize the ulcer with respect to surface area, exudate, and type of wound tissue. Record a sub-score for each of these ulcer characteristics. Add the sub-scores to obtain the total score. A comparison of total scores measured over time provides an indication of the improvement or deterioration in pressure ulcer healing.

LENGTH	0	1	2	3	4	5	Sub-score
X	0	< 0.3	0.3 – 0.6	0.7 – 1.0	1.1 – 2.0	2.1 – 3.0	
WIDTH		6	7	8	9	10	
(in cm²)		3.1 – 4.0	4.1 - 8.0	8.1 – 12.0	12.1 - 24.0	> 24.0	
EXUDATE	0	1	2	3			Sub-score
AMOUNT	None	Light	Moderate	Heavy			
TISSUE	0	1	2	3	4		Sub-score
TYPE	Closed	Epithelial Tissue	Granulation Tissue	Slough	Necrotic Tissue		
							TOTAL SCORE

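### The stratification factor called ulcer size is the total PUSH score, so size is only partly balanced, and the primary comparison does not adjust for it

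*Protocol*

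**What the plan says.** The protocol calls the stratification factor size in four places.

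- Research protocol summary: "Randomisation will be stratified for ulcer size, with cut-off" at a PUSH score of 10 versus 11.
- Section 5.3: "Stratification by wound size (PUSH score up to and including 10 or PUSH score of 11 or higher) will take place".
- Section 6.1.1, first paragraph: "The randomisation will be stratified by ulcer size, with one group being those with a PUSH score of up to and including 10". The second paragraph repeats the statement and names the two lists LOW PUSH and HIGH PUSH.

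Appendix 1 defines the score. The assessor is told: "Categorize the ulcer with respect to surface area, exudate, and type of wound tissue", and then: "Add the sub-scores to obtain the total score".

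Elsewhere the protocol mostly treats size and PUSH as different things. Table 3 in section 5.3 has a wound-grid measurement and a PUSH score as separate week-0 items. Section 5.5.2 and section 8.3 also list them separately. The baseline list in section 8.1 merges them again under ulcer size.

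Section 8.2 sets the primary comparison as the difference in the proportions healed by week 12, with its confidence limit held against -15%. A chi-squared test follows for superiority. The only model that contains baseline ulcer size is the Cox regression in section 8.3, which is secondary and conditional on there being enough data.

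**The concern.** Size is the one characteristic that the protocol chooses to balance, and section 8.3 lists baseline ulcer size as a covariate for healing. If the strata do not separate ulcers by size, the arms can differ in size by chance more than the wording suggests. The primary comparison as described has no other control for it. With 46 patients per arm, the stratification carries that task alone. A reader of the eventual report would also take the strata as size groups, which they are not.

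**Working it through.** **Trial size (context only).** With 50% and 65% healed, a 15-point margin, one-sided 2.5% and 80% power, n per arm = (0.50 x 0.50 + 0.65 x 0.35) x (1.960 + 0.842)² / (0.15 + 0.15)² = 41.6. Then 2 x 41.6 x 1.1 = 91.6, which rounds to the protocol's 92. Nothing below changes it.

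**Composition of the score (Appendix 1).** The maximum total is 10 + 3 + 4 = 17, of which 3 + 4 = 7 points are not size. An open ulcer has a tissue sub-score of at least 1 ("Epithelial Tissue") and at most 4 ("Necrotic Tissue"). Each size band therefore has 4 exudate x 4 tissue = 16 combinations. A total of 11 or more is HIGH.

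| Length x width, cm² | Size sub-score | Range of total | LOW | HIGH |
|---|---|---|---|---|
| 0.7-1.0 | 3 | 4-10 | 16 | 0 |
| 1.1-2.0 | 4 | 5-11 | 15 | 1 |
| 2.1-3.0 | 5 | 6-12 | 13 | 3 |
| 3.1-4.0 | 6 | 7-13 | 10 | 6 |
| 4.1-8.0 | 7 | 8-14 | 6 | 10 |
| 8.1-12.0 | 8 | 9-15 | 3 | 13 |
| 12.1-24.0 | 9 | 10-16 | 1 | 15 |
| over 24.0 | 10 | 11-17 | 0 | 16 |

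The extreme cases are 4 + 3 + 4 = 11 (1.1-2.0 cm², heavy exudate, necrotic tissue: HIGH) and 9 + 0 + 1 = 10 (12.1-24.0 cm², no exudate, epithelial tissue: LOW). Section 6.2.2 typically excludes ulcers below 1 cm², so among entrants it is essentially only those above 24 cm² whose stratum is fixed by size. The counts show what is possible. They are not frequencies, because the 16 combinations are not equally common.

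**How much balance is lost.** The protocol gives no distribution of size, exudate or tissue, so this part rests on assumptions: median area 5 cm², standard deviation of log area 1.1, entry at 1 cm² or more, exudate and tissue uniform, 92 patients, blocks of 10 within strata. The table shows the standard deviation of the between-arm difference in mean log area.

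| Allocation | SD |
|---|---|
| No stratification | 0.197 |
| Total PUSH, up to 10 versus 11 or more | 0.159 |
| Area cut giving strata of the same size | 0.126 |

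The PUSH strata deliver (0.197 - 0.159) / (0.197 - 0.126) = 54% of the available gain. About 22% of patients sit in a different stratum than the area cut would give. If exudate and tissue correlate with area (latent correlation 0.3 to 0.5), the PUSH figure falls to about 0.15 and the misplaced share to 15-18%.

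**What that means for healing.** Assume an odds ratio for healing of 0.5 to 0.7 per log unit of area, so that the log odds ratio is 0.693 to 0.357 in absolute value, and take p(1 - p) as 0.25.

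- Shortfall of PUSH against area strata: (0.159 - 0.126) x 0.25 x 0.357 to 0.693 = 0.3 to 0.6 percentage points.
- A one-SD size imbalance under the PUSH strata: 0.159 x 0.25 x 0.357 to 0.693 = 1.4 to 2.8 points.
- Standard error of the unadjusted difference: square root of [(0.25 + 0.2275) / 46] = 0.102, or 10.2 points.

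**The case against.** The allocation rule itself is clear. All four mentions use the same cut-off, the lists are named after PUSH, and no patient could be put on the wrong list because of the label. Section 6.1.1 gives a practical reason for PUSH: it is routine and quick. Size supplies 10 of its 17 points, and balance on overall ulcer severity is a defensible aim. All of this stands.

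A reader might infer from the table that size is not balanced, since any ulcer from 1.1 to 24 cm² can be in either stratum. That goes too far. At each end it takes one extreme combination out of 16, and total PUSH still tracks size well enough to balance it better than no stratification. A reader might also infer bias, but randomisation within PUSH strata is valid whatever the factor is called. A third inference is that the strata should be redefined by area. The documents do not show that area is the better factor, they give no data to place a cut, and the simulated loss is small. The fear of a misread subgroup result is hypothetical too: sections 8.2 and 8.3 plan no analysis by stratum.

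Finally, covariate adjustment is often left to a statistical analysis plan. That is fair, and if a plan already adjusts for baseline size the analysis part of this point is met. But section 8.2 does not leave the method open; it describes an unadjusted comparison.

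**Conclusion.** The point holds in a limited form. The protocol names the factor wrongly in four places, and size is only partly balanced, with the real overlap at about 3-12 cm². The composition of the score and the band counts are exact from Appendix 1, given an open ulcer. The size of the loss depends on the assumed distributions and odds ratios. The shortfall against area strata is worth well under one percentage point of healing, and a typical leftover size imbalance about 1.4 to 2.8 points, against a standard error near 10 and a margin of 15. The cost is some precision and a mislabelled factor, with no threat to the validity of the allocation. It is worth acting on because grid area is already collected at week 0 and adjustment deals with the leftover imbalance directly.

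**What to change.** Keep the PUSH strata and the existing lists. Then:

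1. Name the factor total PUSH score (ulcer severity) in the summary, in section 5.3 and in both sentences of section 6.1.1. Separate PUSH from grid size in the section 8.1 baseline list.
2. In section 8.2, estimate the primary week-12 healing difference adjusted for PUSH stratum and log baseline grid area. One suitable form is a standardised risk difference from a logistic model, with the lower limit of its 95% confidence interval compared with -15%. Report the unadjusted difference as a sensitivity analysis.

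This needs no new data and leaves the sample size as it is. The cost is a wording amendment and a slightly more complex, model-based primary analysis, which should be fixed before outcome data are seen.

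Stratifying on the PUSH length x width sub-score or on grid area instead is an option only before recruitment starts. It would need new lists and a justified cut that sits well with the cap of 60 per stratum, and it gives up balance on exudate and tissue type.

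### Section 6.1.1 describes two incompatible randomisation schemes, closes a PUSH stratum at 60 (a rule that refuses eligible patients only if the mix is lopsided), and prints its single block size

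*Protocol*

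**What the plan says.** Section 6.1.1 of the protocol opens by saying that patients are allocated "using a non-restricted randomised sequence generated for the whole sample". It then stratifies by PUSH score (10 or below, 11 or above) and says that "a total of 60 randomisations will be generated for each stratification, in blocks of 10 randomisations within said stratification". It spells this out: "This means 6x10 randomisations for LOW PUSH and also 6x10 randomisations for HIGH PUSH".

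The reason given for the list length is the unknown mix: "Since it will not be known up front how many patients will be LOW PUSH or HIGH PUSH". No expected split appears anywhere in the protocol. The consequence of a full list is then stated: "If one of the stratifications reaches 60 then only the other stratification can be recruited into going forward".

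Section 5.2 gives a different recruitment rule: "All eligible patients will be invited to take part until the required numbers have been achieved". The eligibility criteria in sections 6.2.1 and 6.2.2 set no PUSH limit.

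On blinding, section 6.1.1 says that participants cannot be blinded and that the statistical analysis will be. Under section 5.4 the treating nurse measures the ulcer and scores PUSH, and the visiting researcher randomises the patient.

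**The concern.** Three features of one section need attention.

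- **Description.** A non-restricted sequence for the whole sample is simple randomisation from one list. Stratified blocks are restricted randomisation from one list per stratum. Whoever builds the lists or reports the trial cannot follow both.
- **Closing rule.** Not knowing the mix is a reason to make each list long enough for any mix. Here it leads instead to a rule that can shut out patients who meet every eligibility criterion, in a trial whose summary says it takes a pragmatic approach to include a wider cohort. If the rule takes effect, recruitment slows and the sample contains a smaller share of the commoner ulcer severity than the clinics see.
- **Block size.** The only block size is printed in a document that recruiting staff hold, and the bandages look different. Anyone who can follow a list from the start of a block can sometimes work out what comes next, which would open a route to selection at entry. Blinding the analysis does not close that route.

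**Working it through.** **1. The two descriptions.** The opening sentence of 6.1.1 implies one list with no constraint on balance. The later text implies two lists, each balanced within every 10 allocations. The second version is repeated and detailed (two named lists, six blocks of 10 each), so it is the operative one and the opening phrase is the error.

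**2. The recruitment target.** Inputs from section 6.1: 65% v 50% healed, margin 15 points, one-sided alpha 0.025, power 80%, 10% dropout.

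n per arm = (1.96 + 0.8416)² × (0.65×0.35 + 0.50×0.50) / (0.15 + 0.15)² = 7.849 × 0.4775 / 0.09 = 41.6, so 42.

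Total 84; 84 × 1.10 = 92.4, which gives the protocol's 92. (84 / 0.90 = 93.3 would give 94.) I use 92 as the point at which recruitment ends.

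**3. When the closing rule takes effect.** There are 2 × 60 = 120 slots for 92 patients, so at most one stratum can fill before the target. A patient is refused if, among the first 92 eligible and consenting patients, at least 61 fall in one stratum; 60/92 = 65.2%. With p the underlying share of the larger stratum (an assumption, since the documents give none):

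P(any refusal) = P(X ≥ 61) + P(92 − X ≥ 61), X ~ Binomial(92, p).

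Mean refusals come from 20,000 simulated recruitments per row.

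| Share of larger stratum | P(any refusal) | Mean refused before 92 enrolled |
|---|---|---|
| 50% | 0.002 | about 0 |
| 55% | 0.02 | 0.1 |
| 60% | 0.13 | 0.9 |
| 65% | 0.44 | 4.9 |
| 70% | 0.81 | 16 |
| 75% | 0.98 | 36 |
| 80% | >0.99 | 68 |

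As a check where closure is nearly certain: 92 − 60 = 32 patients must come from the smaller stratum, so expected refusals are 32/(1 − p) − 92. That is 36 at 75% and 68 at 80%, matching the simulation.

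In time: section 5.1 plans about 20 months of recruitment, or 92/20 = 4.6 patients a month. If eligible patients arrive at that pace, 36 refusals add 36/4.6, about 8 months.

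**4. Effect on case mix.** After closure the larger stratum is 65.2% of the sample instead of 70%, 75% or 80%. If treatment effects differed between strata by 10 percentage points (an assumption for scale), the pooled difference would move by 0.10 × (70 − 65.2) = 0.5, 0.10 × (75 − 65.2) = 1.0, or 0.10 × (80 − 65.2) = 1.5 points. If effects do not differ, it does not move.

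**5. Predictability.** For a known block of 2m with m per arm and every earlier allocation seen, the expected number fully determined is 2m/(m + 1). With m = 5: 10/6 = 1.67 of 10, or 16.7%. Expected correct guesses are m + (4^m / C(2m, m) − 1)/2 = 5 + (1024/252 − 1)/2 = 6.53 of 10, or 65%, against 50% under simple randomisation. For known blocks of 4 the determined share would be 33%, so 10 is not a small block.

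**The case against.** - **The refusals are conditional.** Nothing in the protocol supports a 70% or 80% share. Ulcers under about 1 cm² are typically excluded, so entry PUSH totals run from roughly 4 or 5 up to 17 and the 10/11 cut falls near the middle. That does not prove an even mix, but it gives no ground for assuming a lopsided one. This stands, and is why the whole range is shown.
- **Section 6.1.1 may simply qualify section 5.2.** A specific rule can limit a general one, and the closing rule is stated openly. That softens the contradiction. It does not explain why the limit is needed, since the stated reason, an unknown mix, is met by longer lists.
- **The predictability figures are ceilings.** They require sight of every earlier allocation in the list and of the position in the block. Allocation follows written consent and is drawn from an online account over two lists. Section 5.1 allows up to two more Trusts, so a single site may see only part of a list. The protocol does not say who can view past allocations. This stands.
- **The wording conflict is editorial.** Largely true, since the operative scheme is clear.

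A reader might go further and infer that eligible patients will be turned away, that the treatment comparison is biased, or that concealment has failed. The documents support none of these. The mix is unknown, allocation within each stratum stays random whether or not a list closes, and nothing shows that recruiting staff can see the sequence.

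**Conclusion.** The point holds in a limited form. The two descriptions of the randomisation are incompatible, and the stratified block scheme is evidently the one intended. The closing rule is an avoidable risk whose size depends on a split the protocol does not give: negligible up to about 55% in one stratum, close to even odds of at least one refusal at 65%, and likely to refuse 16 or more patients from 70% upward. Its consequences are slower recruitment and a shifted case mix. The single published block size allows at most 16.7% of allocations to be deduced and 65% to be guessed, assuming full sight of the list. The sample size, alpha and power are unaffected. The changes are worth making because they amend rules that the protocol itself fixes, at very little cost.

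**What to change.** - Generate at least 92 allocations per stratum (100 is convenient) and delete the sentence that closes a stratum. The probability of refusing an eligible patient for this reason is then zero at any mix, and section 5.2 stands as written.
- Delete the phrase describing a non-restricted sequence for the whole sample, and state stratified permuted blocks.
- Use randomly varying block sizes, kept out of the protocol and away from recruiting staff. The gain comes from the sizes being unknown: smaller blocks whose size was known would be more predictable than the present ones.

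The cost is extending two lists, a few lines of wording, and a possible arm imbalance of a few patients. The present scheme can also leave an imbalance, since either list may stop partway through a block.
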